2.2.5 Quality of Life

The FACT-P, EORTC QLQ-C30/QLQ-PR25, and SHIM questionnaires will be completed at the end of Month 3 and Month 12 or at the time of PSA or radiographic progression (if occurs before Month 12, every effort will be made to obtain the 12-month questionnaires for those who discontinue before 12 months).

2.2.6 Laboratory Assessments

Subjects who experience disease progression (PSA or radiographically) before the end of 12 months should complete laboratory assessments at the Progression Visit as outlined in the Study Schedule. During treatment, laboratory assessments include the following:

- Serum PSA level measured by ultrasensitive assay at the end of each month
- Complete blood count including differential and platelet count at the end of Months 3, 6, 9, and 12 of protocol therapy.
- Total bilirubin, alkaline phosphatase, AST, ALT at the end of Months 3, 6, 9, and 12.
- TSH at the end of Months 3, 6, 9, and 12.
- Fasting glucose, fasting lipid panel (total cholesterol, LDL, HDL, triglyceride), and hemoglobin A1C at the end of Months 3, 6, 9, and 12.
- Peripheral blood collection for measurement of serum testosterone, DHT, estradiol, and fasting serum insulin levels at the end of Months 3, 6, 9, and 12.
- Peripheral blood and urine collection for banking of, serum, plasma, and urine at the end of Months 3, 6, 9, and 12 of protocol therapy (optional).
- Whole blood collected for PAXgene analysis (optional) on Day 1 and end of Month 12

2.2.7 Radiographic Assessments

A whole-body nuclear bone scan, along with cross-sectional imaging of the abdomen/pelvis (CT or MRI) will be obtained as prompted by signs and symptoms of metastatic disease and at the time of PSA progression. DEXA scan measuring BMD at the femoral neck, and lumbar spine will be obtained after 12 months of protocol therapy or at the time of PSA or radiographic progression (if occurs before Month 12, see Progression Visit in Study Schedule).

Subjects who are intolerant of IV CT contrast agents may have CT scans performed with oral contrast or without, if method is identical each time new scans are done. There will be no central reading of the scans and radiographic progression will be based upon investigator assessment.

2.3 Study Period II: Off-therapy Observation Period (Months 13-24)

Subjects without progressive disease (by PSA or radiographic) after 12 months of protocol therapy will stop protocol therapy and enter the Off-therapy Observation Period from Month 13 to Month 24. Continuation of hormonal therapy or initiation of any other of anti-cancer therapy in the absence of PSA or radiographic progression will be considered non-protocol therapy and

will result in study removal. Use of concomitant medications, which may affect serum PSA will not be permitted.

Subjects who develop either PSA or radiographic progression during the Off-therapy Observation Period will have a Progression Visit and be treated as per individual investigator discretion. Efforts will be made to ensure that subjects who develop progressive disease (PSA or radiographic) or discontinue in the absence of progressive disease before 24 months still complete QOL scales after 24 months as prespecified in the study protocol.

2.3.1 Safety Assessment

Subjects will be assessed for adverse events at clinic visits at the end of every 2 months during the Off-therapy Observation Period.

2.3.2 Quality of Life

The FACT-P, EORTC QLQ-C30/QLQ-PR25, and SHIM questionnaires will be completed at the time of progression (PSA or radiographic) or after 24 months.

2.3.3 Laboratory Assessments

Subjects who experience disease progression (PSA or radiographic) before the end of 24 months should complete laboratory assessments at the Progression Visit as outlined in the Study Schedule. During the Off-therapy Follow up Period laboratory assessments include the following:

- Serum PSA level at the end of every 2 months.
- Peripheral blood collection for measurement of serum testosterone levels at the end of every 2 months.
- Fasting glucose, fasting lipid panel (total cholesterol, LDL, HDL, triglyceride), and hemoglobin A1C at the end of Months 18 and 24.
- Peripheral blood collection for measurement of fasting serum insulin at the end of Months 18 and 24.

2.3.4 Radiographic Assessment

A whole-body nuclear bone scan, along with cross-sectional imaging of the abdomen/pelvis (CT or MRI; with IV contrast per individual investigator discretion), will be obtained as prompted by signs and symptoms of metastatic disease and at the time of PSA progression. Subjects who are intolerant of IV CT contrast agents may have CT scans performed with oral contrast or without, as long as method is identical each time new scans are done. There will be no central reading of the scans and radiographic progression will be based upon investigator assessment.

2.4 Follow Up Period (Month 25+)

Subjects without progressive disease (PSA or radiographic) at end of 24 months will enter a Follow-up Period. During this period, subjects will be followed by history and physical exam, serum PSA, and testosterone levels every 3 months. Subjects who develop PSA or radiographic

progression or initiate non-protocol therapy will be removed from study and treated as per individual investigator discretion. If no progressive disease occurred during Months 1 to 24 and it occurs during the Follow-up Period, whole blood RNA and plasma sample collections for biomarker testing should be collected from subjects who consented to this optional sample collection.

3. INTERIM ANALYSIS

No interim analysis will be planned for efficacy due to the expected rate of accrual, the primary endpoint being analyzed, and total sample size. An interim safety review will be performed after 20 subjects have completed at least 1 month of therapy with either apalutamide monotherapy or apalutamide + LHRHa. If there are more than 5 subjects with Grade 3 or higher toxicities not related to ADT (anemia, fatigue, gynecomastia, hot flushes, decreased libido, erectile dysfunction, mood changes, and weight gain), that the study investigator deems as possibly, probably, or definitely treatment-related, the study will be terminated. This indicates that at least 30% of the subjects had unacceptable toxicities. If accrual is completed and all 60 subjects were treated with apalutamide (with or without LHRHa) and if unacceptable toxicity is > 30%, then the exact 95% lower bound for unacceptable toxicity of 30% would be 20.4%. Study enrollment will continue during the interim safety review.

4. SUBJECT INFORMATION

4.1 Demographics and Baseline Characteristics

The following will be summarized by treatment group and overall using the ITT population:

- Age, race, ethnicity, height, and weight.
- Baseline ECOG performance status
- Baseline PSA value
- Number of years since diagnosis of prostate cancer
- Gleason grade/clinical stage/pathologic stage (if prior prostatectomy)/PSA at the time of diagnosis
- Fasting glucose, fasting lipid panel (total cholesterol, LDL, HDL, triglyceride), and hemoglobin A1C
- Use of (neo) adjuvant ADT and time interval since prior ADT (if applicable)
- Type and date(s) of definitive local therapy (radical prostatectomy and/or radiation therapy)
- Time interval from definitive therapy to biochemical relapse to study entry
- PSA doubling time at the time of study entry
- QOL as measured by FACT-P, EORTC QLQ-C30/QLQ-PR25, and SHIM scores at study entry

4.2 Disposition Information

Subject enrollment and disposition will be summarized by treatment group. The summary of subject disposition will display the number of subjects randomized, and the numbers of subjects

in ITT, safety. The summary will also include the number and percent of subjects who completed the study and who discontinued from the study and study treatment, respectively, and reason for discontinuation as documented in the subject status case report form.

4.3 Treatment Compliance and Extent of Exposure

The safety population will be used to summarize drug exposure, treatment compliance, and dose modifications by treatment group.

Treatment duration will be defined as the duration from the date of the first dose of study drug to the date of last dose of study drug. The number of tablets taken will be calculated based on the number of tablets dispensed at the study visits minus the number of returned tablets.

For apalutamide, the overall percent treatment compliance will be defined as the number of tablets taken during the study divided by the expected number of tablets, multiplied by 100. Each subject should be taking a maximum of 4 x 60-mg tablets of study drug per day while on the study. A subject's expected number of tablets will be calculated as the number of assigned tablets per day multiplied by treatment duration.

Choice of specific LHRHa to be used in this study will be per investigator discretion/site practice guidelines. Options include Eligard[®], Lupron Depot[®], Zoladex[®], or Trelstar[®]. Dosing schedule will be per individual investigator discretion. The use of LHRH antagonists (e.g. degarelix) will not be permitted. The LHRHa injections will be delivered either subcutaneously (Eligard[®], Zoladex[®]) or intramuscularly (Lupron Depot[®], Trelstar[®]) by a trained health care provider while on protocol therapy. Subjects with at least one dose modification and the reason for the dose modification will be summarized by treatment group.

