8 STUDY DRUG INFORMATION

8.1 ARN-509

Drug Substance: ARN-509 drug substance is an almost white to slightly brown powder

Chemical Name: (4-[7-(6-cyano-5-trifluoromethylpyridin-3-yl)-8-oxo-6-thioxo-5,7-diazaspiro[3.4]oct-5-yl]-2-fluoro-*N*-methylbenzamide)

Molecular Formula: C₂₁H₁₅F₄N₅O₂S

Molecular Weight: 477.44

Formulation: The ARN-509 tablet supplied for this study contains 60 mg of JNJ-56021927. It will be manufactured and provided under the responsibility of the Sponsor. Refer to the Investigator's Brochure for a list of excipients.

Packaging, Storage, and Labeling: The ARN-509 60-mg tablets will be packaged in 120-count, 160 cc high-density polyethylene (HDPE) bottles with child-resistant caps. Study drug labels will contain information to meet the applicable regulatory requirements

Dose and Administration

ARN-509 will be administered orally on a continuous daily dosing regimen at a dose of 240 mg per day (4 x 60-mg tablets) with or without food.

The switch to tablets for subjects who are receiving softgel capsules will occur at the start of the next cycle (onsite visit). Each softgel capsule contains 30 mg of active drug, and each tablet contains 60 mg of active drug. The conversion from the softgel capsules to the tablet formulation is **2:1** (Table 1).

Table 1 Softgel Capsule to Tablet Conversion

Dose	Number of Softgel Capsules	Number of Tablets
240 mg	8	4
180 mg	6	3
120 mg	4	2

Drug Supply: Study drug will be provided free of charge to subjects enrolled on this study by the company Sponsor. ARN-509 is to be ordered directly from a designee indicated by the study Sponsor.

Dispensing of Drug: Sufficient study drug for the next cycle of therapy will be provided to subjects randomized to one of the two ARN-509 treatment arms at each monthly study visit.

Inventory and Control: The ARN-509 used for this study must be maintained under adequate security and stored in the pharmacy at the study site until dispensing or their destruction at each study site's investigational pharmacy. Investigators may not supply study medication to any person not enrolled in this study or to any person not named as a sub-investigator. In addition,

the investigator must maintain an accurate, running inventory of all drug supplies received and dispensed during conduct of the study.

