2.2.3 Apalutamide

Subjects randomized to either of the two apalutamide-containing arms will receive apalutamide dosed orally on a daily basis with or without food. The starting dose of apalutamide is 240 mg/day. With Amendment 7 (Version 8.0), subjects who are receiving the soft gel capsules will switch to the tablet formulation. Ongoing subjects on a reduced dose of capsules should continue with that dose with lowest allowed dose being 120 mg. Dose delays and dose reductions will be permitted as per guidelines outlined in the study protocol/

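### SAP 4.3 defines apalutamide compliance only in 60-mg tablets, although some men took 30-mg capsules before the Amendment 7 switch, so the literal formula under-reports their compliance.

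*SAP*

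**What the plan says.** SAP 4.3 gives one apalutamide compliance figure per man: "the overall percent treatment compliance will be defined as the number of tablets taken during the study divided by the expected number of tablets", expressed as a percentage. For the numerator, "The number of tablets taken will be calculated based on the number of tablets dispensed at the study visits minus the number of returned tablets". The denominator is the "expected number of tablets will be calculated as the number of assigned tablets per day multiplied by treatment duration". Duration is not split by formulation: "Treatment duration will be defined as the duration from the date of the first dose of study drug to the date of last dose". The section also sets a ceiling: "Each subject should be taking a maximum of 4 x 60-mg tablets of study drug per day while on the study".

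Two unit strengths were used in the trial, and the current text of both documents says so. SAP 2.2.3 states: "With Amendment 7 (Version 8.0), subjects who are receiving the soft gel capsules will switch to the tablet formulation". Protocol 7.5.3 says the same. Protocol 8.1 gives the strengths: "Each softgel capsule contains 30 mg of active drug, and each tablet contains 60 mg of active drug". Table 1 in that section sets 240 mg equal to 8 capsules or 4 tablets, a 2:1 conversion, and has the switch take place at the start of the man's next cycle.

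Neither document says how capsule counts enter the compliance percentage.

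**The concern.** The SAP describes the change of formulation in 2.2.3 and then, in 4.3, gives a formula that cannot accommodate it. The capsule period stays in the denominator, because duration runs from first to last dose, but capsules taken in that period have no place in a numerator made of tablets dispensed minus tablets returned. A man's reported compliance then depends partly on when he enrolled relative to the switch.

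What is at stake is the credibility of a descriptive figure. A reader of the trial report will want to know how fully the men in the two apalutamide arms took their drug, both to interpret a superiority result that is not shown and to judge a non-inferiority claim, where poor adherence can make arms look alike. A compliance percentage that mixes adherence with formulation history does not answer that question.

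**Working it through.** **Inputs**

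- Strengths: capsule 30 mg, tablet 60 mg (Protocol 8.1).
- Units per day at 240 mg: 8 capsules or 4 tablets (Protocol 8.1, Table 1).
- Compliance formula, duration rule and ceiling of 4 tablets per day: SAP 4.3.
- Full course: the 28-, 28- and 35-day visit pattern (SAP section 2, definition of cycle) repeated four times, 4 × (28 + 28 + 35) = 364 days. This length cancels out of every ratio below.
- Share of days on capsules, f: not given in the documents, so shown from 0 to 1.

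**Check of the plan's own figures.** The SAP gives no numerical compliance value to reproduce. Table 1 of Protocol 8.1 is internally correct: 8 × 30 = 4 × 60 = 240 mg; 6 × 30 = 3 × 60 = 180 mg; 4 × 30 = 2 × 60 = 120 mg. Each row is 2:1.

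**Formulas** for a man who takes every dose at 240 mg, with D = 364 days:

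- Literal (capsules left out): 4(1-f)D / 4D = 100(1-f)%.
- Capsules counted one for one as tablets, 4 per day expected: [8fD + 4(1-f)D] / 4D = 100(1+f)%.
- Units assigned at the time (8 capsules, then 4 tablets): [8fD + 4(1-f)D] / [8fD + 4(1-f)D] = 100%.
- mg basis: [30 × 8fD + 60 × 4(1-f)D] / 240D = 100%.

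**Worked case, f = 0.5.** He takes 8 × 182 = 1,456 capsules and 4 × 182 = 728 tablets; 4 × 364 = 1,456 tablets are expected.

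- Literal: 728 / 1,456 = 50%.
- One for one: 2,184 / 1,456 = 150%.
- mg: (30 × 1,456 + 60 × 728) / (240 × 364) = 87,360 / 87,360 = 100%.

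| f | Capsules left out (literal) | Capsules counted as tablets, 4 per day expected | Units assigned at the time | mg basis |
|---|---|---|---|---|
| 0 | 100% | 100% | 100% | 100% |
| 0.25 | 75% | 125% | 100% | 100% |
| 0.5 | 50% | 150% | 100% | 100% |
| 0.75 | 25% | 175% | 100% | 100% |
| 1 | 0% | 200% | 100% | 100% |

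Restricting both numerator and denominator to tablet days also gives 100% for a man who switched. It is undefined (0/0) for a man who took only capsules, and it departs from the stated duration rule.

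The one-for-one reading can also hide missed doses. A capsule-only man who takes half his doses takes 4 capsules a day, so 1,456 / 1,456 = 100% is reported, whereas in mg he is at (30 × 1,456) / 87,360 = 50%.

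**The case against.** The strongest reply is that this is a missing unit convention that a competent programmer would supply. The 2:1 equivalence is in Protocol 8.1, the SAP describes itself as a supplement to the protocol, and values of 150% or 200% would be noticed at once. If the assigned daily number is read as the units assigned at the time, a man who takes every dose scores 100%. All of this is fair, and it limits the seriousness of the point. It does not remove it: SAP 4.3 does not state that reading, its ceiling of 4 tablets per day points away from it, and a plausible-looking 75% would not be noticed as readily as 150%.

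Several stronger conclusions are tempting, and the documents do not support them.

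- A reader might combine the columns and say that compliance could be reported anywhere from 0% to 200%. That merges two incompatible readings. The literal rule gives 0% to 100%; values above 100% arise only if capsules are counted one for one against 4 per day. Both extremes need a man whose whole course was on capsules.
- A reader might call compliance the only evidence of how much drug was received. SAP 4.3 also plans summaries of exposure, treatment duration and dose modifications with reasons, and SAP 6.1 tabulates adverse events leading to dose modification and to discontinuation.
- A reader might add that breaks made under Protocol 9.2 cause men to be scored as non-compliant. A 28-day break does lower the figure to (364 - 28) / 364 = 92.3%, but the SAP sets no compliance threshold and classifies nobody. Keeping interruption days in the denominator is a convention, and dose modifications are summarised separately.
- A reader might infer that the FACT-P result is at risk. The SAP defines no per-protocol set and uses compliance neither as an exclusion nor as a covariate; FACT-P is analysed in the ITT population.

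**Conclusion.** The unit error stands; the rest is convention or interpretation. Followed as written, SAP 4.3 reports a man who took every dose at 100(1-f)%, so a man who switched halfway appears at 50% and a capsule-only man at 0%. For men treated only with tablets, the unit problem does not arise.

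The result rests on two assumptions. The first is that the analysis follows the literal wording and does not silently convert units. The second is that the men concerned had some share of their course on capsules; the current text of both documents shows that such men existed but not how many there were or how long they took capsules. No arm-level mean or median can therefore be derived, and the table describes individuals only. The consequence is confined to one descriptive summary in the safety population for the two apalutamide arms. It should be corrected because a stated rule yields a wrong figure and the remedy is nearly free, not because any inferential result depends on it.

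**What to change.** In SAP 4.3, define compliance in mg:

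- numerator: 30 mg × capsules taken + 60 mg × tablets taken, each as dispensed minus returned;
- denominator: the sum over days of the mg assigned on that day, by formulation and dose period.

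An equivalent definition uses tablet-equivalents, capsules / 2 + tablets, over the assigned tablet-equivalents. Either gives 100% at every f in the table for a man who takes every dose.

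Optionally, state how recorded interruption days enter the denominator, and report relative dose intensity as a separate line so that breaks and reductions remain visible. This is an enhancement, not a correction.

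The cost is a few lines of SAP text and a small programming change. It assumes that capsules dispensed and returned were recorded in the same way as tablets. SAP 4.3 already relies on such counts for tablets, and Protocol 8.1 requires sites to keep a running inventory of all drug supplies. No dose, clinical rule or primary analysis changes.

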9.2 DOSE MODIFICATIONS FOR ARN-509

Inpatient dose interruptions or reductions will be permitted provided that study discontinuation criteria have not been met (Section 7.8).

- Subjects experiencing seizure of any grade or Grade 4 neurotoxicity will have protocol therapy permanently discontinued.
- For subjects experiencing Grades 1-2 treatment-related adverse events, short treatment breaks can be instituted as per the discretion of the Investigator until the severity of the toxicity decreases to Grade 1 or returns to baseline. If toxicity recurs, dose reductions to the next lower dose level will be allowed as per the discretion of the Investigator.
- For subjects experiencing Grade ≥ 3 treatment-related adverse events other than seizure, Grade 4 neurotoxicity or life threatening toxicity, study drug should be held until the severity of the toxicity decreases to Grade 1 or returns to baseline. If toxicity recurs at Grade 3 or higher, the dose of ARN-509 should be reduced to the next lower dose level. A maximum of 2 dose level reductions will be allowed (Table 2).
- Any subject requiring > 28 days delay in treatment due to AEs may meet one of the criteria for study treatment discontinuation (see Section 7.8), which must be discussed with Sponsor.

Table 2 ARN-509 Dose Levels

Total Daily Dose	Number of 60-mg Tablets (QD)
240 mg	4
180 mg	3
120 mg	2

Doses reduced for study treatment-related toxicities should generally not be re-escalated, however, re-escalation back to the previous dose level may be permitted in consultation with the Sponsor.

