2. GENERAL ANALYSIS DEFINITIONS

Study Day: For safety, study day will be calculated in reference to the date of first dose. Study Day 1 corresponds to the date the subject receives first dose of study drug. For efficacy analysis, Study Day will be calculated in reference to the date of randomization.

Cycle: For the purpose of the study, a treatment cycle is defined as 28 days. Subjects will begin taking study drug on Day 1 of Cycle 1. All subjects should be following a 28-day, 28-day, 35-day schedule for their monthly visit (i.e., the 1st post-Day 1 visit is scheduled for 28 days later, the 2nd post-Day 1 visit is scheduled for 28+28 days later, the 3rd post-Day 1 visit is scheduled for 28+28+35 days later, the 4th post-Day 1 visit is scheduled for 28+28+35+28 days later, etc).

Baseline Value: Unless otherwise specified, the baseline value will be defined as the closest measurement prior to or on the day of the first dose of study drug. Change from baseline will be defined as (post-baseline value – baseline value).

Treatment Duration: Treatment duration will be defined as the duration of time from the date of the first dose of study drug to the date of last dose of study drug.

Time to event: Time to event calculations will be defined as the time from randomization to the date of the event of interest. Time to event or duration of event endpoints will be based on the actual date of the event, not visit number or visit label.

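### The tablet-compliance denominator in SAP 4.3 counts directed hold days as days when tablets were due, so a fully adherent man who resumes dosing is reported below 100%

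*SAP*

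**What the plan says.** SAP 4.3 defines percent compliance for apalutamide (ARN-509 in the protocol) as the "number of tablets taken during the study divided by the expected number of tablets, multiplied by 100". The numerator is the "number of tablets dispensed at the study visits minus the number of returned tablets". For the denominator, a subject's "expected number of tablets will be calculated as the number of assigned tablets per day multiplied by treatment duration". Treatment duration is the "duration from the date of the first dose of study drug to the date of last dose of study drug", and SAP section 2 gives the same definition. Neither place removes days without dosing. On the daily count, SAP 4.3 adds: "Each subject should be taking a maximum of 4 x 60-mg tablets of study drug per day while on the study".

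Protocol 9.2 creates days when no tablets are due. For Grade 3 or higher related events, other than those it treats separately, "study drug should be held until the severity of the toxicity decreases to Grade 1 or returns to baseline". For Grade 1–2 related events, "short treatment breaks can be instituted as per the discretion of the Investigator". It also allows up to two dose-level reductions, from 4 to 3 to 2 tablets a day, and possible re-escalation in consultation with the sponsor.

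SAP 4.3 separately summarises, by treatment group, the subjects with at least one dose modification and the reasons.

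**The concern.** The two halves of the ratio treat a hold differently. Tablets not taken during a hold are returned or not dispensed, so they are absent from the numerator. The same days remain in the denominator at the full assigned count. A man who stops and restarts exactly as instructed then shows the same shortfall as a man who missed that many days on his own.

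A second gap concerns dose reductions. The SAP does not say whether the assigned tablets per day are the starting count, the final count or the count in force on each day. Two programmers could produce different percentages from the same data.

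What is at stake is how the by-arm compliance table reads. It would mix instructed interruption with missed doses, and a reader could not separate them from the percentage alone.

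**Working it through.** The documents state no compliance figure, so there is none to reproduce. The check applies the SAP 4.3 formula to a man who takes every tablet he is told to take, uses tablets throughout and returns all unused tablets.

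**Inputs**
- On-therapy length: visits follow a 28-, 28-, 35-day pattern (SAP section 2; Protocol 7.1), so 4 × (28 + 28 + 35) = 364 days, counted inclusively.
- Full dose: 4 tablets a day (SAP 4.3; Protocol 8.1). Expected at full dose: 4 × 364 = 1456 tablets.
- Reduced levels: 3 or 2 tablets a day (Protocol 9.2, Table 2).
- Hold lengths and reduction dates are assumptions. Protocol 9.2 calls the Grade 1–2 breaks short and requires discussion with the sponsor once a delay exceeds 28 days, so holds of 7 to 28 days are shown.

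**Holds, with dosing resumed**

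Reported compliance = 100 × 4 × (364 − h) / (4 × 364), where h is the number of hold days.

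| Hold days | Taken | Expected | Reported |
|---|---|---|---|
| 7 | 1428 | 1456 | 98.1% |
| 14 | 1400 | 1456 | 96.2% |
| 28 | 1344 | 1456 | 92.3% |

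If dosing never resumes, the duration ends at the last dose before the hold, and the hold has no effect.

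**Reduction from 4 to 3 tablets after 91 days, no hold**

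Taken = 4 × 91 + 3 × 273 = 1183.
- Assigned fixed at the starting count: 1183 / (4 × 364) = 1183 / 1456 = 81.2%.
- Assigned fixed at the final count: 1183 / (3 × 364) = 1183 / 1092 = 108.3%.
- Assigned follows the current level: expected = 4 × 91 + 3 × 273 = 1183, giving 100%.

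**Holds and a reduction, with assigned following the dose level**

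Take 63 days at 4, a 28-day hold, 63 days at 4, a 28-day hold, then 182 days at 3. Taken = 4 × 126 + 3 × 182 = 1050. If hold days are still counted at 4, expected = 4 × 182 + 3 × 182 = 1274, and compliance is 1050 / 1274 = 82.4%. The time-varying reading cures the reduction but not the holds, unless the assigned count is also set to zero on hold days.

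**Effect on an arm mean**

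One 28-day hold costs a man 100 − 92.3 = 7.7 points. If, for illustration, 3 of 30 men in an arm each had one, the arm mean would move by 7.7 × 3/30 = 0.77 points. The documents give no expected frequency of holds.

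**The case against.** The strongest reply has four parts.

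1. **Reductions may be handled correctly.** SAP 4.3 calls four tablets a maximum, and Protocol 9.2 expresses each dose level as a tablet count, so a man reduced to 180 mg can fairly be said to be assigned three. A reader might infer that reduced-dose days are certainly miscounted. The text does not support that; it is silent on which count applies. This part of the reply stands.
2. **No one is labelled non-compliant.** A reader might infer that an adherent man would be classed as non-compliant. SAP 4.3 sets no cut-off and no such category. No analysis set in SAP 2.1 depends on compliance. The relevant example of a major deviation in SAP 4.4 is limited to dose modifications outside the protocol's specifications. This stands too.
3. **Toxicity-driven changes are shown elsewhere.** SAP 4.3 summarises dose modifications with reasons, and SAP 6.1 tabulates adverse events leading to dose modification. This helps, but only in part. Those tables count men and events, not days or tablets, so they cannot be used to correct the percentage.
4. **The ratio is a usable descriptive measure.** Tablets taken over the planned dose across the whole span does describe exposure. But that is closer to dose intensity, and the SAP presents it as treatment compliance. The objection therefore favours reporting both quantities under their own names.

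**Conclusion.** The point holds for holds and is conditional for reductions. For a directed hold followed by resumed dosing, the stated rule gives too low a figure for adherence: 98.1%, 96.2% or 92.3% for 7, 14 or 28 days out of 364, where adherence to instructions was 100%. For reductions the plan is under-specified: one fixed count gives about 81% or 108% in the example above, and a count that follows the dose level gives 100%.

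The consequence is minor. Compliance is a descriptive summary of the two apalutamide arms. A reader might infer that it weakens the quality-of-life non-inferiority comparison, but the primary analysis in SAP 5.2.1 is a repeated-measures model in the ITT population with no compliance term, and no endpoint or test uses the percentage. A reader might also infer that the distortion is worse in one apalutamide arm than the other. That would follow if holds were more frequent or longer there, but the documents give no figures on this.

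The sizes assume the full 364-day course, illustrative hold lengths and reduction dates, and complete return of unused tablets.

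**What to change.** In SAP 4.3, define expected tablets as the sum, over each day from first to last dose inclusive, of the tablets prescribed for that day: zero on investigator-directed hold days, and the current count after any reduction or re-escalation. This gives 100% for every example above. Counting both end dates should be stated, because a plain date difference gives 363 days and 1456 / (4 × 363) = 1456 / 1452 = 100.3% for a full course.

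Report dose intensity relative to the starting dose as a separate summary, so that adherence and dose modification are not merged in one number.

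The cost is a short change of SAP wording and modest extra programming. It assumes that the eCRF records dated dose modifications. The documents provide for summarising modifications and their reasons but do not show the dosing fields, so this should be confirmed first. No dosing rule, endpoint or analysis set changes.
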